
Overall Rationale for the Amendment

The protocol was amended in order to add the patient reported outcomes PGI-S and PGI-C.

Section # and Name	Description of Change	Brief Rationale
Section 1.3: Schedule of Activities (SoA) Section 8.1.3.7: Patient Global Impression of Severity (PGI-S) questionnaires	Patient reported outcomes PGI-S and PGI-C were added to the trial.	To enable assessment of psychometric measurement properties of the HESD.
Section 8.1.3.8: Patient Global Impression of Change (PGI-C) questionnaires		
Section 9.3.10: Analysis of PGI-S and PGI-C		
Appendix 5: COVID 19 Pandemic Contingency Plan		
Appendix 8: Abbreviations		
Section 6.8.3: Prohibited medications and procedures	Wash-out period for retinoids and vitamin A in Table 6-2 was corrected.	To avoid discrepancies.
Section 1.3: Schedule of Activities	Weight measurement was added at screening.	Weight is required at screening to calculate renal insufficiency (Cockcroft-Gault formula).
Throughout the document	Minor editorial revisions.	Minor, have therefore not been summarized.

Table of Contents

Title Page	1
Protocol Amendment Summary of Changes Table	3
Table of Contents	5
List of Tables	9
List of Figures	10
1 Protocol Summary	

1.1 Synopsis

Protocol Title: A 24-week, randomised, assessor-blinded, active-controlled, parallel-group, phase 3, 2-arm trial to compare the efficacy and safety of delgocitinib cream 20 mg/g twice-daily with alitretinoin capsules once-daily in adult participants with severe chronic hand eczema

Brief Title: A 24-week trial to compare the efficacy and safety of delgocitinib cream 20 mg/g twice-daily with alitretinoin capsules once-daily in adult participants with severe chronic hand eczema

Sponsor Protocol No.: LP0133-1528

Trial Phase: Phase 3

Sponsor: LEO Pharma A/S

Rationale: There is a clear unmet need for long-term treatment options for patients suffering from moderate to severe chronic hand eczema (CHE). Alitretinoin is the only approved product specifically indicated for treatment of CHE, but it is only indicated for severe CHE and only approved in few countries worldwide. Delgocitinib cream has the potential to become an effective, well-tolerated, and user-friendly treatment for CHE and thereby improve the everyday lives of affected patients. The purpose of this 24-week trial is to compare efficacy, health-related quality of life, and safety of delgocitinib cream and alitretinoin capsules in participants diagnosed with severe CHE.

Objectives and Endpoints and/or Estimands:

Primary Objective

Objectives	Estimand type and strategy	Endpoints
Primary objective: To compare the efficacy and health-related quality of life of twice-daily topical application of delgocitinib cream with once-daily oral administration of alitretinoin capsules in the treatment of patients with severe CHE.	Primary. 'Composite' strategy. First supplementary. 'Pandemic modified composite' strategy. Second supplementary (for endpoints at Week 12 and Week 24). 'Treatment policy' strategy.	 Primary endpoint: Change in HECSI score from baseline to Week 12. Key secondary endpoints: HECSI-90 at Week 12. IGA-CHE TS at Week 12. Change in HESD itch score (weekly average) from baseline to Week 12. Change in HESD pain score (weekly average) from baseline to Week 12. AUC of HECSI-90 from baseline up to Week 24. AUC of change from baseline in DLQI score up to Week 24. Change in HECSI score from baseline to Week 24.

Abbreviations: AUC=area under the curve; CHE=chronic hand eczema; DLQI=Dermatology Life Quality Index; HECSI=Hand Eczema Severity Index; HECSI-90=at least 90% improvement in HECSI score from baseline; HESD=Hand Eczema Symptom Diary©; IGA-CHE=Investigator's Global Assessment for chronic hand eczema©; IGA-CHE TS=IGA-CHE treatment success.

Secondary Objective

Objectives	Endpoints
Secondary objective:	Secondary endpoints:
To compare the safety of twice-daily topical application of delgocitinib cream with once-daily	• Number of treatment-emergent AEs from baseline up to Week 26.
oral administration of alitretinoin capsules in the treatment of patients with severe CHE.	• Number of treatment-emergent SAEs from baseline up to Week 26.
	Number of AEs leading to IMP discontinuation up to Week 24.

Abbreviations: AE=adverse event; CHE=chronic hand eczema, IMP=investigational medicinal product, SAE=serious adverse event.

Exploratory objectives

Exploratory objectives are described in Section 3.

Overall Design:

- This is a phase 3, randomised, assessor-blinded, active-controlled, parallel-group, multi-site, 24-week trial.
- The trial population will consist of adult participants with severe CHE and with a
 documented inadequate response to treatment with topical corticosteroids (TCS) or for whom
 TCS are documented to be otherwise medically inadvisable. The trial will include a
 maximum of 20% of participants with hyperkeratotic subtype.
- Eligible participants will be randomised to receive topical administration of delgocitinib cream 20 mg/g, twice-daily, or oral administration of alitretinoin capsules 30 mg (with an option to reduce to 10 mg during trial conduct), once-daily. Randomisation will be stratified by subtype (hyperkeratotic/non-hyperkeratotic) and region (North America/Europe).
- Participants are not blinded to treatment assignment, but efficacy (Investigator's Global
 Assessment for chronic hand eczema[©] [IGA-CHE[©], hereafter referred to IGA-CHE] and
 Hand Eczema Severity Index [HECSI]) will be evaluated by an assessor blinded to treatment
 assignment. Other assessments will be performed by an unblinded investigator and treatment
 decisions will be made by the unblinded investigator following the recommendation from the
 blinded assessor.
- Certain Contract Research Organisation (CRO) and sponsor staff will also be blinded to ensure the integrity of the trial.

Brief Summary:

The purpose of this trial is to compare the efficacy, health-related quality of life, and safety of delgocitinib cream 20 mg/g twice-daily with alitretinoin capsules 30 mg (with an option to reduce to 10 mg during trial conduct) once-daily in adult patients with severe CHE. The trial duration will be up to 33 weeks. The treatment duration will be up to 24 weeks. The visit frequency will be weekly for the first 3 weeks of treatment and every 4 weeks from Week 4 to the end of treatment.

Number of Participants:

Approximately 510 participants will be randomly assigned to trial treatment in a 1:1 ratio, with 255 evaluable participants per treatment group. Approximately 660 participants will be screened to achieve this target.

Intervention Groups and Duration:

For each participant, the trial will last at least 25 weeks and up to 33 weeks, including:

- a screening period of 1 to 4 weeks (at least 1 visit)
- a treatment period of 24 weeks (9 visits)
- a safety follow-up period of 2 to 5 weeks (1 visit for all participants 2 weeks after the last investigational medicinal product [IMP] dose, plus a pregnancy follow-up visit for woman of childbearing potential [WOCBP] treated with alitretinoin 5 weeks after the last IMP dose)

[figure not shown]
Eligible participants will be randomised in a 1:1 ratio to receive 1 of the following treatments:

- Topical administration of delgocitinib cream 20 mg/g, twice-daily until Week 16, which may continue up to Week 24 depending on clearance status (i.e. IGA-CHE score) and clinical benefit.
- Oral administration of alitretinoin capsules 30 mg (with an option to reduce to 10 mg during trial conduct), once-daily until Week 12, which may continue up to Week 24 depending on clearance status (i.e. IGA-CHE score) and clinical benefit.

Data Monitoring/Other Committee: No

1.2 Schema

Figure 1–1 Trial Design

1. For participants treated with medications requiring a 28-day washout period prior to baseline (see Table 6-2), the duration of the screening period may be extended up to 31 days to ensure appropriate washout.

Abbreviations: HECSI=Hand Eczema Severity Index; IGA-CHE=Investigator's Global Assessment for chronic hand eczema[©].

1.3 Schedule of Activities (SoA)

Table 1-1 Schedule of Activities (SoA)

	6										Follow-	D	Primary	Nominal	Unscheduled	Protocol
	Screen- ing			Tre	atme	nt pe	riod			EOT/ ET ¹	up ²	Pregnancy follow-up ³	endpoint visit at Week 12, it	Week 24 visit, if applicabl	visit, if applicable ⁵	section
Visit	1	2	3	4	5	6	7	8	9	10	11	12	applicable ⁴	e ⁴		
Week	-4 to -1	0	1	2	4	8	12	16	20	24	2 weeks	5 weeks				
Day	-28 ⁶ to -7	1	8	15	29	57	85	113	141	169	after last dose	after last dose				
Visit window (days)	-	-	±3	±3	±3	±3	±3	±3	±3	±3	±3	+6				
Eligibility / baseline assessme	Eligibility / baseline assessments															
Informed consent(s)	X															10.1.3
Participant eligibility	X	X														5.1, 5.2
Demographics	X															8
Fitzpatrick skin type	X															8, Table 8-1
Medical history (including CHE treatment history)	X															8
Classification of CHE (including patch test ⁷)	X														(X) ⁷	8, Table 8-2
Height		X														8
Weight	X	X														8
Treatments and randomisati	on															
Randomisation		X														6.3
Instruction for use of IMP		X														6.2.1
Dispensing of IMP		X			X	X	(X)	(X)	(X)						(X)	6.1
Determination of affected area(s)		X													(X)	6.2.1
New CHE lesions			X	X	X	X	X	X	X	X			X	X	X	6.2.1

	G										E-II	D	Primary	Nominal Wook 24	Unscheduled	Protocol
	Screen- ing			Tre	atme	nt pe	riod			EOT/ ET ¹	Follow- up ²	Pregnancy follow-up ³	endpoint visit at Week 12, if	Week 24 visit, if applicabl	visit, if applicable ⁵	section
Visit	1	2	3	4	5	6	7	8	9	10	11	12	applicable ⁴	e ⁴		
Week	-4 to -1	0	1	2	4	8	12	16	20	24	2 weeks	5 weeks				
Day	-28 ⁶ to -7	1	8	15	29	57	85	113	141	169	after last dose	after last dose				
Visit window (days)	-	-	±3	±3	±3	±3	±3	±3	±3	±3	±3	+6				
Delgocitinib cream topical application		Twice-daily for 16 weeks							Stop/re s nece							6.2.1.1
Alitretinoin capsules oral administration		Once	e-dail	y for 1	12 we	eks			p/resta ecessa							6.2.1.2
Treatment compliance (eDiary)			Daily ⁸													6.4
Return of treatment and accountability					X	X	X	(X)	(X)	(X)					(X)	6.4
Concomitant medication and concurrent procedures	X	X	X	X	X	X	X	X	X	X	X		X	X	X	6.8
Blinded assessor assessment	of efficacy															
HECSI		X	X	X	X	X	X	X	X	X			X	X	(X)	8.1.1
IGA-CHE	X	X	X	X	X	X	X	X	X	X			X	X	(X)	8.1.2
Participant assessments of ef	ficacy at h	ome														
eDiary handout/training 8	X															8.1.3.1
HESD					Da	ily 8							Daily ⁸	Daily 8		8.1.3.1
Return of eDiary										X 9				X 9		8.1.3.1
Participant assessments of ef	ficacy and	health	-rela	ted q	uality	of li	fe dur	ing tri	ial visi	ts						
HEIS		X	X	X	X	X	X	X	X	X			X	X		8.1.3.3
DLQI		X	X	X	X	X	X	X	X	X			X	X		8.1.3.2
EQ-5D-5L		X			X	X	X	X		X			X	X		8.1.3.4
TSQM					X		X			X			X	X		8.1.3.5
WPAI-CHE		X			X		X			X			X	X		8.1.3.6
PGI-S ¹⁰		X		X	X	X	X									8.1.3.7

	Screen-										Follow-	Pregnancy	Primary	Nominal	Unscheduled	Protocol
	ing			Tre	eatme	nt pe	riod			EOT/ ET ¹	up 2	follow-up ³	endpoint visit at Week 12, if	Week 24 visit, if applicabl	visit, if applicable ⁵	section
Visit	1	2	3	4	5	6	7	8	9	10	11	12	applicable ⁴	e ⁴		
Week	-4 to -1	0	1	2	4	8	12	16	20	24	2 weeks	5 weeks				
Day	-28 ⁶ to -7	1	8	15	29	57	85	113	141	169	after last dose	after last dose				
Visit window (days)	-	-	±3	±3	±3	±3	±3	±3	±3	±3	±3	+6				
PGI-C ¹¹				X	X	X	X									8.1.3.8
Participant assessment of safe	ety															
Participant assessment of local tolerability (delgocitinib group only)			We	eekly	while	on tr	eatme	nt ¹²		X						8.2.7.1
Unblinded investigator assess	ments of s	safety														
Physical examination	X									X					(X)	8.2.1
Vital signs	X	X								X					(X)	8.2.2
ECG	X		X							X					(X)	8.2.3
Fasting ¹³ triglycerides and cholesterol (central laboratory)	X	X			X	X	X	X	X	X	X				(X)	8.2.4, 10.2
Chemistry, haematology (central laboratory) 13	X	X			X	X	X	X	X	X	X				(X)	8.2.4, 10.2
Serology, total IgE (central laboratory)	X															8.2.4, 10.2
Urinalysis (urine dipstick)	X	X				X	X	X		X					(X)	8.2.4, 10.2
Urine pregnancy test (WOCBP only)	X	X			X	X	X	X	X	X	X 14	X ³	X	X	(X)	8.2.5, 10.2
Check contraception compliance (alitretinoin group only)	X	X			X	X	X	X	X	X	X	X	X	X	(X)	8.2.5
Mental health interview ¹⁵	X	X			X	X	X	X	X	X					(X)	8.2.6

	Screen- ing			Tre	atme	nt pe	riod			EOT/ ET ¹	Follow- up ²	Pregnancy follow-up ³	Primary endpoint visit at Week 12, if	Nominal Week 24 visit, if applicabl	Unscheduled visit, if applicable ⁵	Protocol section
Visit	1	2	3	4	5	6	7	8	9	10	11	12	applicable ⁴	e ⁴		
Week	-4 to -1	0	1	2	4	8	12	16	20	24	2 weeks	5 weeks				
Day	-28 ⁶ to -7	1	8	15	29	57	85	113	141	169	after last dose	after last dose				
Visit window (days)	-	-	±3	±3	±3	±3	±3	±3	±3	±3	±3	+6				
Local tolerability according to investigator (delgocitinib group only)			X	X	X	X	X	X	X	X					(X)	8.2.7.2
AEs	X	X	X	X	X	X	X	X	X	X	X		X	X	X	8.3, 10.3
Optional assessments (at selec	cted sites o	only)														
Photography of both hands back and front including the wrist ¹⁶		X					X	X		X						8.1.4
End of treatment/trial																_
End-of-treatment form										X						8.10.1
End-of-trial form ¹⁷										(X)	X	X		(X)	(X)	8.10.2

- 1. End-of-treatment assessments will be conducted at Week 24. Participants who permanently discontinue the IMP or who withdraw from the trial prior to Week 24 will be asked to return to the trial site for an ET visit as soon as possible after the last dose for completion of all trial procedures scheduled for the visit at Week 24.
- 2. All participants will be asked to return to the trial site approximately 2 weeks after the last dose of IMP for assessment of safety at a follow-up visit.
- 3. For WOCBP treated with alitretinoin, only.
- 4. Participants who permanently discontinue the IMP prior to Week 12 will be asked to return to the trial site at Week 12 for a primary endpoint visit and at Week 24 for a nominal Week 24 visit. Participants who permanently discontinue the IMP between Week 12 and Week 24 will be asked to return to the trial site for a nominal Week 24 visit.
- 5. Unscheduled visits occur if participants need to make a visit in between the scheduled visit dates, e.g. for reading of a patch test, due to an AE, or due to a significant change in their disease state. Assessments to be performed at unscheduled visits will be at the discretion of the unblinded investigator.
- 6. For participants treated with medications requiring a 28-day washout period prior to baseline (see Table 6-2), the duration of the screening period may be extended up to 31 days to ensure appropriate washout. For WOCBP the duration of the screening period may be extended up to 42 days to ensure compliance with contraceptive and pregnancy prevention programme requirements.
- 7. For participants who have not had a patch test within 3 years prior to screening, the patch test should be completed so results are available prior to baseline assessments (Day 1).

- 8. Completion of the HESD component of the eDiary will be initiated at least 1 week prior to baseline (Day 1), but preferably from the date the participants receive the eDiary. Compliance with the eDiary completion will be reviewed by the trial site staff throughout the trial. Participants who permanently discontinue the IMP but remain in the trial will continue completing the eDiary until the nominal Week 24 visit.
- 9. Not applicable at the ET visit if the participant does not withdraw from the trial, as participants who discontinue IMP but remain in the trial will continue completing the eDiary until the nominal Week 24 visit.
- 10. Includes Itch PGI-S, Pain PGI-S, and HESD PGI-S.
- 11. Includes Itch PGI-C, Pain PGI-C, and HESD PGI-C.
- 12. While on treatment with delgocitinib cream 20 mg/g, local tolerability will be evaluated weekly by the participants in the eDiary from Day 7 onwards up to End of Treatment/Early Termination visit.
- 13. Participants should be fasting for at least 8 hours prior to collection of laboratory samples.
- 14. For WOCBP treated with delgocitinib, only.
- 15. After baseline, mental health interview is required only for the alitretinoin group.
- 16. Photography will require additional informed consent. If deemed necessary (e.g. in case of poor quality), photographs can be retaken at the next visit.
- 17. An end-of-trial form must be completed for all screened participants at the participant's last trial visit. For participants who discontinue IMP prematurely, the end-of-trial form will be completed at the nominal Week 24 visit, if this visit occurs after Visit 11 or Visit 12 (if applicable). For WOCBP treated with alitretinoin, the end-of-trial form must be completed at Visit 12 (pregnancy follow-up). For all other participants, the end-of-trial form must be completed at Visit 11 (follow-up).

Abbreviations: AE=adverse event; CHE=chronic hand eczema; DLQI=Dermatology Life Quality Index: ECG=electrocardiogram; eDiary=electronic diary; EQ-5D-5L=EuroQoL 5-Dimension Health Questionnaire 5-Level; EOT= end-of-treatment; ET=early termination; HECSI=Hand Eczema Severity Index; HEIS=Hand Eczema Impact Scale®; HESD=Hand Eczema Symptom Diary®; IGA-CHE=Investigator's Global Assessment for chronic hand eczema®; IgE=immunoglobulin E; IMP=investigational medicinal product; PGI-C = Patient Global Impression of Change; PGI-S = Patient Global Impression of Severity; TSQM=Treatment Satisfaction Questionnaire for Medicine; WOCBP=woman of childbearing potential; WPAI-CHE=Work Productivity and Activity Impairment – Chronic Hand Eczema.

2 Introduction

Delgocitinib is a pan-Janus kinase (JAK) inhibitor that is being developed as a cream for the treatment of inflammatory skin disorders, such as CHE.

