2.3.3 Overall Benefit/Risk Conclusion

Taking into account the measures taken to minimise risk for the trial participants, the potential risks identified in association with delgocitinib and alitretinoin are justified by the anticipated benefits that may be afforded to participants with severe CHE, and more generally the potential benefits to patients with moderate to severe CHE in the future.

3 Objectives and Endpoints

Table 3-1 Primary Objective and Estimands for Primary Endpoint and Key Secondary Endpoints

Objectives	Estimand type and strategy	Endpoints
Primary objective: To compare the efficacy and health-related quality of life of twice-daily topical application of delgocitinib cream with once-daily oral administration of alitretinoin capsules in the treatment of patients with severe CHE.	Primary. 'Composite' strategy. First supplementary. 'Pandemic modified composite' strategy. Second supplementary (for endpoints at Week 12 and Week 24). 'Treatment policy' strategy.	Primary endpoint: Change in HECSI score from baseline to Week 12. Key secondary endpoints: HECSI-90 at Week 12. IGA-CHE TS at Week 12. Change in HESD itch score (weekly average) from baseline to Week 12. Change in HESD pain score (weekly average) from baseline to Week 12. AUC of HECSI-90 from baseline up to Week 24. AUC of change from baseline in DLQI score up to Week 24. Change in HECSI score from baseline to Week 24.

Abbreviations: AUC=area under the curve; CHE=chronic hand eczema; DLQI=Dermatology Life Quality Index; HECSI=Hand Eczema Severity Index; HECSI-90=at least 90% improvement in HECSI score from baseline; HESD=Hand Eczema Symptom Diary©; IGA-CHE=Investigator's Global Assessment for chronic hand eczema©; IGA-CHE TS=IGA-CHE treatment success.

Table 3-2 Secondary and Exploratory Objectives and Endpoints

Objectives	Endpoints				
Secondary objective: To compare the safety of twice-daily topical application of delgocitinib cream with once-daily oral administration of alitretinoin capsules in the treatment of patients with severe CHE.	 Secondary endpoints: Number of treatment-emergent AEs from baseline up to Week 26. Number of treatment-emergent SAEs from baseline up to Week 26. Number of AEs leading to IMP discontinuation up to Week 24. 				
Exploratory objectives:	Exploratory endpoints:				

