8.2.6 Mental Health Monitoring

Depression, depression aggravated, anxiety, aggressive tendencies, mood alterations, psychotic symptoms, and very rarely, suicidal ideation, suicide attempts and suicide have been reported in patients treated with systemic retinoids, including alitretinoin.

All participants treated with alitretinoin should be monitored for signs of depression and referred for appropriate treatment if necessary.

Prior to initiation of alitretinoin and at each visit during treatment, participants should be asked about any psychiatric disorder, depression, or mood disturbance in a mental health interview, as outlined in the SoA (Table 1-1).

Participants should stop alitretinoin if they develop depression, mood disturbance, psychosis, or aggression, as described in Section 7.1. However, discontinuation of alitretinoin may be insufficient to alleviate symptoms and therefore further psychiatric or psychological evaluation may be necessary. Awareness by family or friends may be useful to detect mental health deterioration.

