8.2.7 Local Tolerability

For participants receiving delgocitinib cream only, an assessment of local tolerability will be provided by the participant and by the investigator, according to the SoA (Table 1-1).

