8.2.7.1 Participant's Assessment of Local Tolerability

The participant will complete a weekly assessment of stinging/burning in connection with the delgocitinib cream applications in the eDiary. The participant will be asked to retrospectively assess the worst stinging/burning in connection with the delgocitinib cream application during the last week. In addition, the participant will be asked by the unblinded investigator at the End of Treatment/Early Termination visit to assess the local tolerability during the last week (see Section 1.3). The assessment will be done using the 4-point scale shown in Table 8-8.

Table 8-8 Participant's Assessment of Local Tolerability after Delgocitinib Cream Application

Grade (severity)	Stinging/burning				
0 (none)	No stinging or burning.				
1 (mild)	Slight warm, tingling sensation, not really bothersome.				
2 (moderate)	Definitive warm, tingling sensation, that is somewhat bothersome.				
3 (severe)	Hot, tingling/stinging sensation that has caused definite discomfort.				

The participant's assessment of local tolerability may be reported as an AE at the discretion of the investigator, even if the investigator does not suspect a local skin reaction related to the application of delgocitinib cream (reporting of e.g. pain or stinging/burning by the participant).

For the participant's assessment of local tolerability at the EOT/ET visit, the highest (worst) skin reaction score across treatment area(s) will be recorded in the eCRF.

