8.3.2 Method of Detecting AEs and SAEs

Care will be taken not to introduce bias when detecting AEs and/or SAEs. Open-ended and non-leading verbal questioning of the participant is the preferred method to inquire about AE occurrence.

At all visits, participants will be asked a non-leading question by the investigator about AEs, e.g.: 'How have you felt since I saw you last?'. Participant-reported local tolerability will be

queried specifically (see Section 8.2.7.1) and reported as AE(s) if deemed relevant by the investigator.

When completing the TSQM PRO questionnaire, participants will be asked direct questions about side effects. If the participant answers 'yes' for item 3, and/or tick anything but 'not applicable' for items 4, 5 or 6 (see Section 8.1.3.5), the investigator must follow-up with the participant to ensure AEs are appropriately recorded.

If the AE qualifies as an SAE, expedited reporting is required (see Section 10.3.4). It is important that the investigator also observes the participant for any changes not reported by the participant and records these changes.

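### After baseline, psychiatric symptoms are asked about directly only in the alitretinoin arm, so psychiatric adverse events are not ascertained alike in the two arms

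*Combined protocol and SAP*

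**What the plan says.** Table 1-1 (Section 1.3) marks the mental health interview at screening, baseline and Weeks 4, 8, 12, 16, 20 and 24. Footnote 15 then limits it: "After baseline, mental health interview is required only for the alitretinoin group". Section 8.2.6 gives the content: "participants should be asked about any psychiatric disorder, depression, or mood disturbance in a mental health interview". This is a direct question about named symptoms, put by staff who know the treatment.

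Comparing safety between the arms is the secondary objective. Its endpoints (Section 3, Table 3-2) include "Number of treatment-emergent AEs from baseline up to Week 26" and the number of AEs that lead to stopping the IMP. Section 9.3.11.1 tabulates events by system organ class and preferred term, and does not distinguish prompted from unprompted events.

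On detection, Section 8.3.2 states: "Care will be taken not to introduce bias when detecting AEs and/or SAEs". It prefers open, non-leading questions and uses one in both arms at every visit.

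**The concern.** If one arm is asked directly about mood at visit after visit and the other is not, more of the mood events that occur will be found in the arm that is asked, even when the true incidence is the same. Those events enter the tables that serve the safety objective, and a reader will take a difference in psychiatric events as a difference between the drugs.

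The open-label design adds weight to this. Only HECSI and IGA-CHE have a blinded assessor (Sections 4.2 and 6.3). For AEs, asking both arms in the same way is one of the few protections left.

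There is also a route to a second endpoint. Section 7.1 (item 6) makes mood disturbance and related symptoms a ground for permanent discontinuation on alitretinoin only. A finding from the interview can therefore also become an AE leading to IMP discontinuation. The rule itself is not in question here; the point is only that detection feeding it is arm-specific.

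**Working it through.** **The plan's own figure.** The one planning calculation (Section 9.5) concerns the primary endpoint. With a difference of 7.5, SD 30 and 1-sided 2.5%, n per arm = 2 × (1.960 + 0.842)² × (30/7.5)² = 252. At 255 per arm the power is 80.6%. The stated 80% is reproduced. This point does not depend on it and does not alter it.

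**Occasions for detection after baseline**

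| Method | Alitretinoin | Delgocitinib |
|---|---|---|
| Open AE question (8.3.2) | every visit | every visit |
| TSQM side-effect items with AE follow-up (8.1.3.5, 8.3.2) | Weeks 4, 12, 24 | Weeks 4, 12, 24 |
| Mental health interview (Table 1-1, footnote 15) | Weeks 4, 8, 12, 16, 20, 24 (6) | 0 |

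Six is a maximum. It applies to a participant who stays on the visit schedule to Week 24, and Section 8.2.6 describes the interviews as taking place during treatment.

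**Route into the tables.** No section says how an interview finding becomes an AE. The general rule in Section 8.3 applies: events reported by the participant or observed by the investigator are recorded.

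**Illustration of size.** The documents give neither an incidence of mood events nor capture probabilities, so all of these are assumptions: equal true incidence p in both arms (3%, 6%, 10%), capture 90% when asked, and 40% to 80% when volunteered. The arm size of 255 is from Section 9.5.

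Detected participants = 255 × p × capture. Gap = p × (0.90 − volunteered capture).

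| p | Asked | Volunteered | Gap, participants | Gap, percentage points |
|---|---|---|---|---|
| 3% | 6.9 | 3.1 to 6.1 | 0.8 to 3.8 | 0.3 to 1.5 |
| 6% | 13.8 | 6.1 to 12.2 | 1.5 to 7.7 | 0.6 to 3.0 |
| 10% | 23.0 | 10.2 to 20.4 | 2.6 to 12.8 | 1.0 to 5.0 |

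**Carry-over to the share with any AE.** A participant who already has another AE adds nothing to that share. If a fraction q has another AE, independently of mood events, the gap becomes (1 − q) × p × (0.90 − volunteered capture). With q assumed at 40% to 60%, the extremes are 0.4 × 0.3 = 0.1 and 0.6 × 5.0 = 3.0 points. The effect on this overall percentage is thus smaller than on psychiatric events.

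**The case against.** The case on the other side has several parts.

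- The interview is safety monitoring specific to alitretinoin (Section 2.3.1, Table 2-1; Section 8.2.6), not a tool for comparing arms. That explains why it exists. Its findings still enter the compared tables.
- Detection common to both arms is substantial: the open question and the TSQM items. Both arms also answer the EQ-5D-5L anxiety/depression item, although nothing links that answer to AE recording. This stands as dilution; it does not remove the difference.
- Exclusion criterion 11 removes recent psychiatric disorders, so incidence may be low. This stands, and is one reason to treat the size as unknown.
- AE counts are outside the testing hierarchy (Section 9.1), and psychiatric AEs are neither an endpoint nor one of the specific AE summaries. This stands. Alpha, power and sample size are untouched.
- Tabulation by system organ class shows psychiatric events separately, so a careful reader can set them aside. This stands in part, but nothing in the visible text tells the reader to do so.
- Participants and investigators know the treatment, so equal interviews would not make AE reporting fully alike. This also stands: the fix removes one source of bias, not all.
- Section 9 refers to a more detailed SAP. No separate SAP text is among the documents, so a provision there cannot be excluded.

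A reader might infer more from the delgocitinib side: "For participants receiving delgocitinib cream only, an assessment of local tolerability will be provided by the participant and by the investigator". Participants also answer a weekly question: "The participant will complete a weekly assessment of stinging/burning in connection with the delgocitinib cream applications in the eDiary". It is tempting to call this a mirror-image bias, so that two prompts act in opposite directions and the net effect is lost. The documents do not support that. Alitretinoin participants apply no study cream or vehicle (Section 4.2), so they have no application events to miss and nothing to be asked about. The answers also do not turn into AEs automatically: "The participant's assessment of local tolerability may be reported as an AE at the discretion of the investigator". The tolerability questions are not part of this point.

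**Conclusion.** The point holds for psychiatric AEs. After baseline their ascertainment differs between arms by design, and nothing in the visible text corrects for it. The between-arm comparison of these events is therefore not like for like. Total treatment-emergent AEs and AEs leading to IMP discontinuation are affected less, and by an unknown amount.

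Under the stated assumptions the spurious gap in participants with a detected mood event is 0.3 to 5.0 percentage points. That range shows what is possible; it is not an estimate.

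A reader might go further and say that the AE counts must differ between arms. That does not follow: ascertainment differs by design, while the counts may or may not. Nor does the schedule plainly contradict Section 8.3.2, which calls open questioning the preferred method and does not make it the only one. The consequence is limited to how descriptive safety results can be read. It is a cheap improvement, not a flaw in the confirmatory analysis.

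**What to change.** Change footnote 15 of Table 1-1 and Section 8.2.6 so that, for data collection, the same interview questions are asked in both arms at the Week 4, 8, 12, 16, 20 and 24 visits. Leave the discontinuation rules as they are. The cost is a few minutes at six existing visits in the delgocitinib arm, with no new visit or staff. Because the mood-related discontinuation criterion would still apply to alitretinoin only, AEs leading to IMP discontinuation could still differ through that rule; the change equalises detection only.

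If this is not adopted, add to Section 9.3.11.1 a summary of total treatment-emergent AEs, and one of AEs leading to IMP discontinuation, that leave out the psychiatric system organ class in both arms. State beside the psychiatric results that ascertainment was unequal after baseline. The cost is two tables and a note, and Section 9 allows the SAP to be revised before database lock.

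Do not use a table restricted by how each event was detected. It would drop alitretinoin events found at interview even where the participant would have volunteered them, and keep comparable delgocitinib events. In the 6% example, alitretinoin could keep close to 0 of 13.8 participants while delgocitinib keeps 6.1 to 12.2, which is the opposite bias.
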